7.2.1. Criteria for Starting Subsequent Treatment Cycles

Prior to the start (within 48 hours) of each treatment Cycle (Day 1) the following parameters **MUST** be met:

- ANC \geq 1,000/mm³
- Platelet count \geq 100,000/mm³ (transfusion independent, defined as no platelet transfusion within 7 days and recovery from nadir)
- Does not meet PD or treatment interruption/discontinuation criteria

In addition, subjects **MUST** meet the following within 24 hours prior to the start of each treatment cycle:

- Confirmation of negative serum or urine pregnancy test (sensitivity of at least 25 mIU/mL) in FCCBP/FCBP.
- Confirmation of the use of 2 forms of effective birth control for FCCBP/FCBP and sexually mature males or confirmation of commitment to complete abstinence.
- Completion and documentation of required pomalidomide education and counseling.

If a subject does not meet the above parameters by Day 28 of a treatment cycle, then the subsequent cycle should not be started until these parameters are met. Refer to Section 7.2.2 for dose interruptions/reductions or next cycle delays due to count recovery or non-hematological toxicities.

7.2.2. Dose Reductions, Interruptions and Discontinuation Criteria for Toxicities

Hematological and non-hematological toxicity will be graded using CTCAE version 4.03. In all cases, the reason for dose modification/interruption/discontinuation must be recorded in the subject's medical record. If the subject discontinues the protocol-prescribed therapy due to an AE, this event must be reported in accordance with the procedures outlined in Section 10.

Subjects who experience significant toxicity as listed below (Table 8) will have pomalidomide interrupted or reduced as specified in Table 7. Up to two dose reductions of pomalidomide are allowed across the Treatment Period in the event of specific protocol defined toxicity with no evidence of disease progression.

In addition:

- If a subject experiences a toxicity that requires interruption and does not recover until Day 22, pomalidomide (dose-reduced) should be restarted on Day 1 of the subsequent cycle if other protocol parameters are met.
- The dose will not be re-escalated following a dose reduction, even if there is minimal or no toxicity with the subsequent reduction in dose.
- Subjects who again experience dose modifying toxicity after 2 dose reductions will be taken off pomalidomide therapy.

- Subjects who experience hematologic toxicity (eg, neutropenia or thrombocytopenia) should have appropriate laboratory testing at least twice weekly (3 to 4 days apart) until the toxicity has resolved.
- If there is a > 14-day delay in starting the subsequent cycle for a pomalidomide-related toxicity, the investigator should consider pomalidomide dose reduction or pomalidomide discontinuation, based upon clinical judgment and the required dose modification criteria outlined in [Table 8](#).

Table 7: Dose Reductions of Pomalidomide

Dose Level	Dose
Starting dose	2.6 mg/m ² /day
Dose Level -1	1.9 mg/m ² /day
Dose Level -2	1.3 mg/m ² /day
Dose Level -3	Discontinue treatment

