7.2. Treatment Administration and Schedule

The starting dose of pomalidomide will be 2.6 mg/m²/day, based on the subject's actual BSA calculated at the beginning of each cycle. Pomalidomide (oral capsules or suspension) will be administered daily for the first 21 days of every 28-day cycle and only enough pomalidomide for 1 cycle (21-day supply) of treatment will be dispensed on Day 1 of each new cycle of therapy. The oral suspension is available for use in subjects who are unable to swallow the capsules or at the discretion of the Investigator. On Day 1 of each cycle, pomalidomide will be dispensed and administered after completion of all clinical procedures required for that day. Subsequent pomalidomide administration (ie, Days 2-21 of each cycle) may occur at the subject's home.

Pomalidomide will not be administered on Days 22 through 28 of the 28-Day treatment cycle even if a subject experiences a toxicity that requires dose interruption (see Section 7.2.2). Counting of days should continue uninterrupted and the rest period (Days 22 to 28) should be continued as planned. For example, if a subject experiences a toxicity that requires interruption and does not recover until Day 22, pomalidomide should be restarted on Day 1 of the subsequent cycle if other protocol parameters are met. Subjects will continue treatment for up to 24 cycles or until documented PD, withdrawal of consent/assent, treatment becomes intolerable or death, whichever comes first.

For subjects receiving capsules, the pomalidomide dose should be calculated and rounded up or down to the nearest 0.5 mg as the prescribed dose before each new dosing cycle. The dose

prescribed should be based on the subject's BSA and yield the minimum number of capsules to achieve the prescribed dose. However, if a subject is unable to swallow larger capsules, varying appropriate strength combinations may be considered during medication assignment.

Pomalidomide capsules should not be broken, chewed or opened and should be taken at approximately the same time every day for 21 consecutive days in a cycle. If a dose is vomited within 15 minutes of taking the dose and the capsule(s) are visible in the emesis, the dose should be repeated and the Investigator should be notified to have replacement capsule(s) provided. If vomiting occurs beyond 15 minutes of dosing, do not repeat the dose and that day's dose should be skipped. Any vomiting of the capsules should be described in the subject dosing diary.

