7.2.2.1. Dose Modifications

Table 8: Dose Modification Criteria

Toxicity	Dose Modification and Discontinuation
Grade 4 neutropenia that occurs during the 21-day dosing period Grade 3 or 4 febrile neutropenia Grade 4 neutropenia of ≥ 5 days duration during the treatment rest period	
 • Interrupt pomalidomide until the neutrophil count recovers to ≥ 1000/mm³ and no fever (≤ 38.3 °C) (if applicable). • If the toxicity resolves and the subject meets eligibility parameters to resume as described in the protocol within 14 days (eg, ANC ≥ 1000/mm³; platelets ≥ 100,000/mm³), the subject should re-initiate treatment at one dose level lower. • If the dose modifying toxicity does not resolve to meet the parameters as described in the protocol within 14 days of treatment being held, pomalidomide should be permanently discontinued.
Grade 3 or 4 platelet count decreased that occurs during the 21 day dosing period	
 • Transfuse platelets to a post-transfusion plate target of ≥ 100,000/μL if platelet count is < 50,000/mm³. • Interrupt pomalidomide until the platelet count recovers to ≥ 100,000/mm³ unsupported (defined as no platelet transfusion within 7 days and recovery from nadir). • If the toxicity resolves and the subject meets eligibility parameters to resume as described in the protocol within 14 days (eg, ANC ≥ 1000/mm³; platelets > 100,000/mm³), the subject should re-initiate treatment at one dose level lower. • If the toxicity does not resolve to meet the eligibility parameters as described in the protocol within 14 days of treatment being held, pomalidomide should be permanently discontinued.

Table 8: Dose Modification Criteria (Continued)

Toxicity	Dose Modification and Discontinuation

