Any Grade 4 non-hematological toxicity related to pomalidomide Any Grade 3 non-hematological toxicity related to pomalidomide with the specific exclusion of following: 
 • Grade 3 nausea and vomiting controlled by anti-emetics (≤ 3 days) • Grade 3 fever or infection (≤ 3 days) • Grade 3 hypophosphatemia, hypokalemia, hypocalcemia or hypomagnesemia responsive to oral supplementation 	
 • Interrupt pomalidomide until toxicity returns to baseline or \leq Grade 2. • If the toxicity resolves and the subject meets eligibility parameters to resume as described in the protocol within 14 days the subject should re-initiate treatment at one dose level lower. • If the toxicity does not resolve to \leq Grade 2 or meet the eligibility parameters as described in the protocol within 14 days of treatment being held, the investigator, based on clinical judgment, should consider discontinuing pomalidomide permanently.
Any other medically significant or sufficiently intolerable AEs \geq Grade 2 related to pomalidomide that requires treatment interruption	Interrupt pomalidomide until resolution of symptoms. 
 • If resolves ($<$ Grade 2) ≤ 3 days, the subject may resume treatment at the same pomalidomide dose level. • If the toxicity recurs upon drug re-challenge, treatment should be interrupted again until the toxicity resolves ($<$ Grade 2), and subject should re-initiate treatment at a lower dose level. • If the \geq Grade 2 toxicity recurs at the lower dose level and is considered medically significant or intolerable, pomalidomide should be interrupted again until the toxicity resolves ($<$ Grade 2), and the subject should re-initiate at the next lower dose level. • If the \geq Grade 2 toxicity recurs after two dose reductions (Dose level -2) and is considered medically significant or intolerable, pomalidomide should be permanently discontinued. • If the toxicity resolves ($<$ Grade 2) after > 3 days but ≤ 14 days, subject may resume treatment at a lower dose level. • If the toxicity does not resolve ($<$ Grade 2) within 14 days of treatment being held, the investigator, based on clinical judgment, should consider discontinuing pomalidomide permanently.
Grade 4 rash or blistering, Steven's Johnson or TEN (toxic epidermal necrolysis) or anaphylaxis	Pomalidomide should be discontinued permanently.

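### Section 7.2.2 and Table 8 differ on whether a dose level is lost when a short hold ends on Day 22

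*Protocol*

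**What the plan says.** Four places in the protocol bear on a toxicity that recovers on Day 22.

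- **Section 7.2.2**, in the list that supplements Table 8: if a toxicity that required interruption "does not recover until Day 22, pomalidomide (dose-reduced) should be restarted on Day 1 of the subsequent cycle", on condition that the remaining protocol requirements are satisfied. There is no carve-out by grade, type of toxicity or length of hold. The same section allows at most two reductions and rules out going back up afterwards.
- **Section 7.2** gives the same case as an example of how cycle days are counted: if the toxicity "does not recover until Day 22, pomalidomide should be restarted on Day 1 of the subsequent cycle if other protocol parameters are met". It does not mention dose level, and it refers to Section 7.2.2 for interruptions.
- **Table 8 (Section 7.2.2.1)** makes the action depend on the toxicity and on time.
  - Other related adverse events of Grade 2 or higher: if resolved in 3 days or less, "the subject may resume treatment at the same pomalidomide dose level". If resolved later but within 14 days, the subject may resume at a lower level. Beyond 14 days, the investigator "should consider discontinuing pomalidomide permanently".
  - Neutropenia and platelet rows: if recovered within 14 days, "the subject should re-initiate treatment at one dose level lower". If not resolved "within 14 days of treatment being held, pomalidomide should be permanently discontinued".
  - Related Grade 3 or 4 non-hematologic toxicity: one level lower if resolved within 14 days; beyond that, stopping is left to the investigator's judgment.
- **Section 7.2.1** lists what must be true before each cycle starts, including: "Does not meet PD or treatment interruption/discontinuation criteria".

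**The concern.** Section 7.2.2 attaches a reduced dose to every interruption that ends on Day 22. Table 8 does not: one row permits the same dose after a short hold, and the hematologic rows end treatment after a long one. No sentence says whether the Day 22 instruction overrides Table 8 or yields to it.

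Day 22 is a likely date for recovery to be documented. Table 4 schedules hematology and chemistry on Day 22 of Cycles 1 and 2, and dosing stops after Day 21 in any case.

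At stake is a step that cannot be undone. A level given up under one passage and not the other stays lost, and it uses one of only two permitted reductions. Two sites treating identical events could therefore give different doses from then on. The exposure and dose-reduction summaries in SAP Sections 9.5 to 9.7 would partly reflect which paragraph each site followed.

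**Working it through.** The plan gives no figure to reproduce. The check takes every possible first day of a hold, fixes recovery on Day 22, and compares the two sets of instructions.

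**Inputs**
- Dosing days 1 to 21, no dosing on Days 22 to 28 (Section 7.2).
- Table 8 cut-offs: 3 days or less; more than 3 and up to 14 days; more than 14 days.
- Dose levels 2.6, 1.9 and 1.3 mg/m²/day (Table 7); capsule doses by body surface area (Table 12).

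**Assumptions.** Both the 3-day and the 14-day limits are counted from the first held dose. The protocol ties the 14 days to treatment being held but does not say how either limit is counted. With first held day h, hold length = 22 − h (doses missed). The variant that counts both end days is 23 − h.

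**Result with 22 − h**

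| First held day | Hold (days) | Other related AE, Grade 2 or higher | Hematologic rows | Related Grade 3/4 non-hematologic row |
|---|---|---|---|---|
| 19-21 | 3 to 1 | Table 8 permits same level; 7.2.2 says reduced: **differ** | Both lower: agree | Both lower: agree |
| 8-18 | 14 to 4 | Both lower: agree | Both lower: agree | Both lower: agree |
| 1-7 | 21 to 15 | Stopping left to judgment: no contradiction | Table 8 says stop; 7.2.2 read alone says restart reduced: **differ on the bare wording** | Stopping left to judgment: no contradiction |

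With 23 − h the three bands become Days 20-21, 9-19 and 1-8. Under either count, no hold falls in both the short and the long band.

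**Extent.** The short-hold difference covers 3 of 21 possible first held days (2 of 21 on the inclusive count), in one row of Table 8. The long-hold difference covers 7 of 21 (8 of 21), in the hematologic rows only.

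**Dose at stake in the short-hold case, first reduction**
- Nominal: (2.6 − 1.9) / 2.6 = 0.7 / 2.6 = 26.9%, or 27%.
- Capsules at 1.00 m²: Table 12 gives 2.5 mg at the starting level (band 0.87-1.05 m²) and 2.0 mg at Level -1 (band 0.93-1.18 m²). (2.5 − 2.0) / 2.5 = 20%. Rounding to capsule strengths explains the gap from 27%.

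**Long-hold case, passages side by side.** The Section 7.2.2 restart is conditional on other protocol parameters being met. Section 7.2.1 makes it a condition of every new cycle that the subject meets no discontinuation criterion. A hematologic toxicity unresolved after 14 days of holding meets the Table 8 criterion for a permanent stop. Read together, these allow a consistent result in which the criterion applies. The reader has to assemble it from three places.

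**The case against.** **The same-dose option is only permissive.** Table 8 says the subject may resume at the same level, so a site that reduces satisfies both passages. That is true, and it makes the conflict softer than two opposed commands. It does not remove it: Section 7.2.2 uses should, so a site that takes up the Table 8 option departs from Section 7.2.2.

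**The long-hold case is already settled.** The condition in Section 7.2.2 together with Section 7.2.1 largely answers it, and this stands. What remains is that the sentence does not say so. Section 7.2.2 does call the Table 8 criteria required, but in an item about a delay of more than 14 days in starting the next cycle. A subject who recovers on Day 22 can start on time, so that item does not reach this case.

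**Section 7.2 is a third, full-dose rule.** A reader might infer this because the words on reduction are absent there. The documents do not support it: the sentence illustrates day counting, is silent on dose, and refers to Section 7.2.2. It adds ambiguity, not a separate contradiction.

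**The primary endpoint depends on this.** A reader might infer that too. SAP Section 6.1.1 requires 6 completed cycles (3 for DIPG) for long-term stable disease, so an earlier permanent stop would close that route. But that belongs to the long-hold case, where a consistent reading exists. In the short-hold case treatment continues, and a reduced dose does not disqualify a subject under the SAP definition.

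**Conclusion.** The point holds for short holds. For an other related adverse event of Grade 2 or higher, held from Day 19, 20 or 21 and resolved on Day 22, Section 7.2.2 and Table 8 give different answers on whether a dose level is lost, and nothing in the text settles it. The size is one irreversible level: from the starting dose, 27% nominally, or 20% in capsules at 1.00 m². The affected days rest on counting missed doses from the start of the hold; an inclusive count leaves Days 20-21.

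The hematologic long-hold case is secondary: a gap in wording for which Section 7.2.1 supports a consistent reading.

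Two stronger conclusions are tempting and should not be drawn. First, that one child could be kept at full dose, reduced or stopped depending on the passage read. The short and long bands do not overlap and involve different rows, so each case has two outcomes, not three. Second, that 10 of the 21 dosing days carry contradictory instructions. That sum (3 + 7) adds days from different toxicity rows; for any one row the count is 3, 7 or none.

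This is an inconsistency of wording with a permanent dosing consequence. It is not a flaw in the two-stage design or its operating characteristics.

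**What to change.** The sponsor must reconcile the Day 22 sentences in Sections 7.2 and 7.2.2 with Table 8 and Section 7.2.1. The text should state which passage governs the restart dose, or discontinuation, when recovery falls on Day 22, and should use the same words in both sections. It would help to state at the same time how the 3 and 14 days are counted. The choice of rule belongs to the sponsor's clinical team; this review does not say which is right.

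The cost is about one clarifying sentence in each of the two sections, carried in the next amendment. Visits, drug supply and sample size are unchanged.

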7.2.2.1. Dose Modifications

Table 8: Dose Modification Criteria

Toxicity	Dose Modification and Discontinuation
Grade 4 neutropenia that occurs during the 21-day dosing period Grade 3 or 4 febrile neutropenia Grade 4 neutropenia of ≥ 5 days duration during the treatment rest period	
 • Interrupt pomalidomide until the neutrophil count recovers to ≥ 1000/mm³ and no fever (≤ 38.3 °C) (if applicable). • If the toxicity resolves and the subject meets eligibility parameters to resume as described in the protocol within 14 days (eg, ANC ≥ 1000/mm³; platelets ≥ 100,000/mm³), the subject should re-initiate treatment at one dose level lower. • If the dose modifying toxicity does not resolve to meet the parameters as described in the protocol within 14 days of treatment being held, pomalidomide should be permanently discontinued.
Grade 3 or 4 platelet count decreased that occurs during the 21 day dosing period	
 • Transfuse platelets to a post-transfusion plate target of ≥ 100,000/μL if platelet count is < 50,000/mm³. • Interrupt pomalidomide until the platelet count recovers to ≥ 100,000/mm³ unsupported (defined as no platelet transfusion within 7 days and recovery from nadir). • If the toxicity resolves and the subject meets eligibility parameters to resume as described in the protocol within 14 days (eg, ANC ≥ 1000/mm³; platelets > 100,000/mm³), the subject should re-initiate treatment at one dose level lower. • If the toxicity does not resolve to meet the eligibility parameters as described in the protocol within 14 days of treatment being held, pomalidomide should be permanently discontinued.

Table 8: Dose Modification Criteria (Continued)

Toxicity	Dose Modification and Discontinuation
Any Grade 4 non-hematological toxicity related to pomalidomide Any Grade 3 non-hematological toxicity related to pomalidomide with the specific exclusion of following: 
 • Grade 3 nausea and vomiting controlled by anti-emetics (≤ 3 days) • Grade 3 fever or infection (≤ 3 days) • Grade 3 hypophosphatemia, hypokalemia, hypocalcemia or hypomagnesemia responsive to oral supplementation 	
 • Interrupt pomalidomide until toxicity returns to baseline or \leq Grade 2. • If the toxicity resolves and the subject meets eligibility parameters to resume as described in the protocol within 14 days the subject should re-initiate treatment at one dose level lower. • If the toxicity does not resolve to \leq Grade 2 or meet the eligibility parameters as described in the protocol within 14 days of treatment being held, the investigator, based on clinical judgment, should consider discontinuing pomalidomide permanently.
Any other medically significant or sufficiently intolerable AEs \geq Grade 2 related to pomalidomide that requires treatment interruption	Interrupt pomalidomide until resolution of symptoms. 
 • If resolves ($<$ Grade 2) ≤ 3 days, the subject may resume treatment at the same pomalidomide dose level. • If the toxicity recurs upon drug re-challenge, treatment should be interrupted again until the toxicity resolves ($<$ Grade 2), and subject should re-initiate treatment at a lower dose level. • If the \geq Grade 2 toxicity recurs at the lower dose level and is considered medically significant or intolerable, pomalidomide should be interrupted again until the toxicity resolves ($<$ Grade 2), and the subject should re-initiate at the next lower dose level. • If the \geq Grade 2 toxicity recurs after two dose reductions (Dose level -2) and is considered medically significant or intolerable, pomalidomide should be permanently discontinued. • If the toxicity resolves ($<$ Grade 2) after > 3 days but ≤ 14 days, subject may resume treatment at a lower dose level. • If the toxicity does not resolve ($<$ Grade 2) within 14 days of treatment being held, the investigator, based on clinical judgment, should consider discontinuing pomalidomide permanently.
Grade 4 rash or blistering, Steven's Johnson or TEN (toxic epidermal necrolysis) or anaphylaxis	Pomalidomide should be discontinued permanently.
Non-central line related thromboembolic event	Pomalidomide should be discontinued permanently.

AEs = adverse events; ANC = absolute neutrophil count.

7.2.3. Overdose

Overdose, as defined in this protocol, refers to pomalidomide dosing.

On a per dose basis, an overdose is defined as the following amount over the protocol-specified dose of pomalidomide assigned to a given subject, regardless of any associated AE(s) or sequelae.

- $> 10\%$ over the protocol-specified dose.

On a schedule or frequency basis, an overdose is defined as anything more frequent than the protocol-required schedule or frequency.

Complete data about treatment administration, including any overdose, regardless of whether the overdose was accidental or intentional, should be reported in the eCRF. See Section 10 for the reporting of AEs associated with overdose.

7.3. Method of Treatment Assignment

Subjects will be enrolled (Section 6.1.5) into the study via IRT. For detailed IRT screening and enrollment procedures, please refer to the IRT User Manual. Subjects will enroll and be assigned to one of 4 parallel strata based on the following tumor types: high-grade glioma, medulloblastoma, ependymoma and DIPG.

7.3.1. Subject Numbering

All subjects will be screened and subsequently enrolled into the study using IRT. The Investigator or designated site staff will be assigned password protected, coded identification numbers that give them authorization to log into IRT. At screening, the Investigator or designated staff will log into the IRT and provide the requested identifying information for the subject. IRT will then confirm the assignment of a 2-part unique subject ID number consisting of 7 digits. The first part is a 3-digit site number and the second part is a 4-digit number (always starting with “1” for the initial screening) assigned sequentially to subjects at that site (eg, 101-1001, 101-1002, etc). If the subject is not eligible for enrollment into the study, the site is required to register the subject as a screen failure in IRT. Subjects who fail screening may be rescreened at the Investigator’s discretion. For subjects who are rescreened, a new ICF/IAF will need to be signed and screening procedures will need to be repeated (if rescreening occurs > 28 days from original screening date). A new Subject ID will be issued once the rescreening transaction is registered in IRT. To identify subjects that rescreen, the 4-digit number identifier will start with “2” (eg, 101-2001) for 2nd rescreen, “3” (eg, 101-3001) for third rescreen, etc.

Once the subject is enrolled into the study, the subject will retain their Subject ID number which will be used to identify that specific subject during participation in the study.

